#### **8.1.10 Side effects**

Refer to the current investigator's brochure for toxicity information.

### **9.0 EXPLORATORY STUDIES**

MRD analysis will be conducted using PCR methods and results will be compared over time (four time-points total). In addition, we will correlate results with PFS and OS. At Northwestern University, the Pathology Core Facility (PCF) Clinical Trials staff will be responsible for procuring, processing, and shipping all samples (tissue and peripheral blood) for exploratory studies. Participating sites should use whatever local services they have available to handle this aspect.

### **9.1 Sample Collection & Processing Guidelines**

#### **9.1.1 Tissue**

Archived tissue from a previous biopsy will be obtained from all patients who have it available at baseline (lack of available tissue for exploratory studies will not preclude patients from participating in this study – however it is not *optional* for those who do have tissue available). Approximately 3-5 unstained FFPE slides (from diagnosis or time of high disease load) will be procured. Each slide should be 5-10 microns (or equivalent) in thickness; slides may be stored at ambient temperature until shipment.

#### **9.1.2 Peripheral Blood**

Three peripheral blood samples for exploratory studies will be collected at baseline (prior to treatment on Cycle 1 Day 1), after 1 month of treatment, 6 months of treatment, and approximately 18-24 months post-first dose of treatment. All study blood samples will be collected at the same time as blood is being drawn for routine care/tests. Two samples will be collected using lavender-top EDTA Vacutainer® sample collection tube. Label the tube with the date of the draw, patient ID number, and patient initials. Using the labeled, lavender-top EDTA Vacutainer® sample collection tube, approximately 10cc of blood will be drawn. Tubes should be gently inverted 8 times to ensure adequate mixing of the anticoagulant. Blood samples may be stored at ambient temperature for up to 24 hours.

Within 24 hours of sample collection, perform cell preparation using Ficoll protocol on one of the EDTA tubes. Isolate peripheral blood mononuclear

cells (PBMCs). Store PBMCs at -80C until shipment (see lab manual for details).

For the second sample of peripheral blood, flow cytometry will be performed, as standard of care at the treating institution. The results of the flow cytometry will be interpreted as positive or negative per the treating investigator and recorded for comparison with simultaneous results of MRD testing by PCR.

A third optional sample will be collected in a 6mL EDTA tube for future research that involves evaluating the treatment response by analyzing changes in the proportion of tumorigenic clones within the patient's blood as compared to the initial biopsy. These samples will be stored in PCF Clinical Trials Unit (CTU). Such future research must be reviewed and approved by Janssen prior to use of the samples.

## **9.2 Shipping Instructions**

See separate lab manual for instructions on shipping both tissue and peripheral blood samples.

## **9.3 Assay Methodology**

Baseline tissue slides will be used to identify clones. All peripheral blood samples will undergo MRD analysis testing using PCR methods. Analysis will be performed by an outside laboratory that is contracted for these services (see separate lab manual for details).

# **10.0 STATISTICAL CONSIDERATIONS**

## **10.1 Study Design/Study Endpoints**

### **10.1.1 Primary Endpoint**

Progression-free survival (PFS) will be defined as the absence of disease progression or death from any cause. The rate of PFS will be calculated after 3 years.

### **10.1.2 Secondary Endpoints**

Adverse events will be defined according to the National Cancer Institute's Common Terminology Criteria for Adverse Events (NCI CTCAE) version 4.03. The occurrence and severity of each will be recorded. The rate of conversion from PR to CR will be calculated. Overall survival (OS) will be assessed after 4 years.

### **10.1.3 Exploratory Endpoints**

Minimum residual disease (MRD) will be quantified as being either categorical or continuous.

## **10.2 Sample Size and Power Calculations**

The primary endpoint is three-year PFS. Our null hypothesis is that ibrutinib maintenance will yield no improvement upon the 60% three-year PFS observed in

studies described above. We consider an observed three-year PFS of 80% both feasible and of significant clinical improvement. The study will have 10% Type I error and 90% power to detect an effective treatment using a one-stage design based on the true proportion of patients achieving 3-year PFS is at least 80% versus the null hypothesis that the true complete response rate is at most 60%.

Based upon these parameters, our sample size will be 36 evaluable patients. For the final analysis, if 25 or fewer patients are alive and without progression from among all 36 evaluable patients accrued, we will consider this regimen ineffective for this patient population. If, on the other hand, 26 or more patients are alive and without progression, this will be considered sufficient evidence that this treatment may be recommended for further testing in subsequent studies, particularly in a randomized setting.

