## STUDY SCHEMA

Patients must receive at least 4 cycles of induction chemotherapy with or without auto-SCT, including R-CHOP (with or without alternating R-DHAP), R-Hyper-CVAD, or R-bendamustine.

Per Cheson 2007 criteria.

During treatment, 1 cycle = 28 days. Patients will be evaluated (and drug will be dispensed) prior to each cycle for the first 6 months, then every 3 cycles thereafter for the remainder of treatment. See section 4.2 for the provision of 6-month visits after 2 years.

Follow-up schedule for patients off-treatment will be every 3 months up to 2 years post-first dose, then every 6 months up to 4 years post-first dose. Date of progression will be documented as well.

Study Numbers: NU 14H06  
PCI-32765MCL2003Initial version: September 24, 2014  
AMD 11: ver. date 08.06.2022**STUDY SUMMARY**

Title	A Phase II Clinical Trial Evaluating Ibrutinib Maintenance Following Intensive Induction for Patients with Previously Untreated Mantle Cell Lymphoma (MCL)
Version Date	August 8, 2022 (Amendment 11)
Phase/Design	Phase II, single-arm, multicenter, open-label study
Study Center(s)	Lead site: Northwestern University Participating sites: University of Michigan, University of Utah, and Dana Farber d/b/a Massachusetts General Hospital
Objectives	
Primary objective: Determine the 3-year PFS in patients with previously-untreated MCL who achieve response to intensive induction therapy and then receive maintenance Ibrutinib.
 
Secondary objectives:
 
 
• Toxicity
 
• Rates of conversion from PR to CR
 
• Median overall survival at 4 years
 
 
Exploratory objectives: Monitor MRD results by PCR and correlate with PFS and OS.

Sample Size	36 evaluable patients (patients who receive < 1 complete cycle of therapy will not be considered evaluable for efficacy endpoints and will be replaced; we estimate this to represent 3 or fewer subjects)

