### 3.0 SELECTION OF SUBJECTS

The target population for this phase II study is patients with histologically confirmed (previously untreated) mantle cell lymphoma (MCL) who have achieved response (CR or PR) to intensive induction systemic chemotherapy (with or without ASCT). This will be a multicenter trial conducted at Northwestern University. Northwestern University will serve as the lead site and coordinating center for this study. Participating sites will include University of Utah, and Dana Farber d/b/a Massachusetts General Hospital.

A total of 36 *evaluable* subjects will be needed for this trial (defined as having received  $\geq$  1 complete cycle of treatment). Approximately 5 potentially eligible patients are seen per month, and it is anticipated that at least 2 per month will be accrued *once the protocol is open and enrolling at all sites*. Potential patients may be referred to the Principal Investigator (PI) at Northwestern University or to the local PI at each participating site.

Eligibility will be evaluated by the study team according to the following criteria. Eligibility waivers are not permitted. Subjects must meet all of the inclusion and exclusion criteria to be registered to the study. Study treatment may not begin until a subject is registered. Please refer to Section 11.4 for complete instructions regarding registration procedures.

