#### **4.8 Removal of Patients from Therapy and/or Study as a Whole**

Patients can be removed from the study treatment (follow-up permitted) and/or from the study as a whole (no follow-up permitted) at any time at their own request, or they may be withdrawn at the discretion of the investigator for safety, behavioral or administrative reasons. The reason(s) for discontinuation must be documented on the appropriate eCRF and may include:

- Patient voluntarily withdraws from *treatment* (follow-up continues)
- Patient withdraws *consent* (termination of treatment *and* follow-up)
- Patient is *unable to comply* with protocol requirements (termination of treatment, follow up continues)
- Patient demonstrates *disease progression* (termination of treatment, follow-up continues). Clinical suspicion of progressive disease (PD) or loss of response should be investigated radiographically, and will result in removal of active therapy if confirmed by clinical investigation.

Study Numbers: NU 14H06  
PCI-32765MCL2003

Initial version: September 24, 2014  
AMD 11: ver. date 08.06.2022

- Patient experiences *toxicity* that makes continuation in the protocol unsafe (termination of treatment, follow up continues)
- Treating physician determines that continuation on the study would *not be in the patient's best interest* (termination of treatment, follow up continues)
- Patient becomes *pregnant*, see section 7.2.6 for reporting timeframe (termination of treatment, but follow up continues)
- Patient develops a second malignancy (except for basal cell carcinoma or squamous cell carcinoma of the skin) that requires treatment, which would interfere with this study (termination of treatment, but follow up continues).  
NOTE: Patients who stop treatment in order to receive other anti-cancer therapy for a second malignancy may, on a case-by-case basis and upon approval of PI and DMC, be considered for possible re-start of study medication once other anti-cancer therapy is complete. See Section 4.3.1 for more details.

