Comprehensive chemistry panel, Mg, and LDH. Comprehensive chemistry panel includes glucose, calcium, albumin, ALT, AST, sodium, potassium, total bilirubin, alk phos, creatinine.

If applicable for WOCBP (urine or serum).

Baseline/screening tests required to be completed as follows: within 90 days prior to registration for imaging, bone marrow biopsy and EGD/Colonoscopy (if applicable) and within 14 days prior to registration for all other baseline assessments (except informed consent, which can be signed within 30 days prior to registration).

Imaging should be performed at baseline, after cycles 3 and 6, every 6 months/cycles for the first 2 years, once at 3 years, and as clinically indicated thereafter (including EOT, as clinically appropriate, for patients who complete 4 years of therapy, or patients that come off study treatment early for a reason other than progression). In general, it is *preferred* that imaging be CT-based; at a minimum, the same modality should be used consistently for each patient.

Ibrutinib will be administered at a dose of 560 mg PO daily throughout the course of treatment unless a dose reduction occurs (see section 4.3.2 for details).

Patients will be asked to keep a study calendar for the duration of treatment See section 4.2 for details on dispensing and visit frequency.

Patients will be evaluated on Day 1 of each cycle ( $\pm 2$  days) for the first 6 cycles (prior to the start of each cycle). NOTE: Cycle 1 Day 1 should begin within 14 days after registration, however Day 1 labs (hematology and chemistry tests) need only be repeated if screening labs were performed  $>7$  days prior to C1D1.

Patients will be evaluated every 3 cycles (on Day 1,  $\pm 10$  days) beginning with cycle 7. After 2 years on therapy, patients will continue to be seen *clinically* every 3 cycles, however collection of data for study purposes will only be required every 6 cycles (approximately every 6 months) for the remainder of study treatment.

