**Patients who complete 4 years** of maintenance therapy with ibrutinib will have one final follow-up study visit approximately 30 days post-last dose. **Patients who discontinue study therapy prior to this point** will be followed up to a maximum of 4 years (post-first dose of treatment) for survival endpoints only (no labs or physical exam are required), including date of progression. Follow-up will occur until progression at the following times: every 3 months ( $\pm 10$  days) up to 2 years after the first dose of treatment and then every 6 months ( $\pm 10$  days) thereafter up to 4 years after the first dose of treatment.

Physical exam includes height (baseline only), weight, 12-point symptom assessment and vitals (bp, heart rate, temperature)

Bone marrow biopsy is only required (within 90 days of registration) for those with documented bone marrow involvement of MCL at time of last bone marrow biopsy. These patients should have repeat bone marrow biopsy after 6 cycles of therapy, in order to judge efficacy of treatment, then as clinically indicated during the period of follow up. If no previous bone marrow biopsy was obtained (e.g. at time of diagnosis), or if disease involvement was resolved as of most recent bone marrow biopsy, then none is required for trial entry, however it may be done at the discretion of the treating investigator.

Only required (within 90 days of registration) for those with documented involvement of MCL by EGD and/or colonoscopy, at time of last EGD/colonoscopy.

These patients should have repeat EGD/colonoscopy with biopsy after 6 cycles of therapy, in order to judge efficacy of treatment, then as clinically indicated during the period of follow up. If no previous EGD/colonoscopy was obtained (e.g., at time of diagnosis), or if disease involvement was resolved as of most recent EGD/colonoscopy with biopsy, then none is required for trial entry, however it may be done at the discretion of the treating investigator.

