### **10.3 Planned Analyses**

#### **10.3.1 Primary Objective**

The primary objective will be to determine the progression-free survival (PFS) rate after 2 and 3 years. This will be done in two ways. First, the proportion of patients alive and progression-free at 2 and 3 years will be calculated, along with an exact 90% confidence interval, both two-sided as well as a lower 90% confidence limit. The number of patients alive and progression-free at 2 and 3 years will be used to address the primary hypothesis as indicated in section 10.2 above. In addition, a Kaplan-Meier curve will be calculated to obtain the actuarial estimate of two-year progression-free survival.

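### The primary endpoint is three-year PFS, but Section 10.3.1 plans Kaplan-Meier only at two years and sends the two-year count to the same rule, and the 36 patients are defined in two ways

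*Combined protocol and SAP*

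**What the plan says.** Sections 2.1, 6.1 and 10.2 all make three-year PFS the primary endpoint. Section 10.2 sets a one-stage design of 60% against 80%, with 10% type I error, 90% power and 36 evaluable patients. The decision is a count: "if 25 or fewer patients are alive and without progression from among all 36 evaluable patients accrued, we will consider this regimen ineffective"; 26 or more supports further testing.

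Section 10.3.1 says how the endpoint is analysed. First, "the proportion of patients alive and progression-free at 2 and 3 years will be calculated, along with an exact 90% confidence interval", both two-sided and as a lower limit; no denominator is named. It then uses the number progression-free at both 2 and 3 years for the primary hypothesis, referring back to 10.2. Finally, "a Kaplan-Meier curve will be calculated to obtain the actuarial estimate of two-year progression-free survival". No three-year Kaplan-Meier estimate, confidence limit for the PFS curve or PFS censoring rule is given. For overall survival, Section 10.3.2 does ask for 90% limits.

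Three places say who the 36 are:

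- Study Summary, Sample Size: patients with less than one complete cycle "will not be considered evaluable for efficacy endpoints and will be replaced", an estimated 3 or fewer.
- Section 3.0: 36 evaluable subjects "will be needed for this trial (defined as having received" at least one complete cycle).
- Section 6.1: a single dose makes a patient evaluable for PFS.

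On unknown status, Section 4.8 lets patients leave "from the study as a whole (no follow-up permitted) at any time at their own request". Footnote 7 of Section 5.0 schedules imaging "every 6 months/cycles for the first 2 years, once at 3 years, and as clinically indicated thereafter". Footnote 11 follows patients who stop treatment early "for survival endpoints only (no labs or physical exam are required), including date of progression", and the schedule marks no scan in the Follow-Up column. No section says how an unknown 3-year status is scored.

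**The concern.** The analysis section should deliver the quantity that the design section tests, in the population for which the cut-off was derived. Here it does not, in three respects.

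1. **Time point of the estimate.** Kaplan-Meier is the only planned PFS method that can use a patient with incomplete follow-up, and it is specified at a time that is not the primary endpoint.
2. **Two counts, one cut-off.** Nobody progression-free at 3 years can have progressed by 2 years. With complete data the 2-year count is therefore at least as large as the 3-year count, and 26 is at least as easy to reach. The 60% null and the error rates belong to three years only.
3. **Population.** The cut-off of 26 controls type I error for 36 patients. If a different number enters the count, or the interval uses a different set from the count, the stated error rates no longer describe the decision.

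A smaller, related gap is that a patient of unknown 3-year status has no written score, so the 90% power is stated without its condition of complete 3-year data.

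**Working it through.** **Inputs.** From 10.2: n = 36, success if X ≥ 26, null 0.60, alternative 0.80. From the Study Summary: up to 3 replaced patients. The rate of unknown 3-year status is not given; 1 to 3 of 36 is assumed for illustration.

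**Step 1: reproduce the design.** Exact binomial, all 36 outcomes known:

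- Type I error: P(X ≥ 26 | 36, 0.60) = 0.0904.
- Power: P(X ≥ 26 | 36, 0.80) = 0.9111.

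The stated design reproduces. The exact (Clopper-Pearson) one-sided lower 90% limit, the 0.10 quantile of Beta(x, n − x + 1), is 60.5% for 26/36 and 57.6% for 25/36. With 36 as denominator, the count rule and the planned lower limit therefore agree about the 60% null.

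**Step 2: the two definitions of the 36.** Suppose replacement takes place, so that 36 patients complete a cycle, and the replaced patients are also counted under Section 6.1, each with the same chance of success. With the cut-off kept at 26:

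| Patients counted | P(X ≥ 26 given 0.60) | Exact lower 90% limit at 26/n |
|---|---|---|
| 36 | 9.0% | 60.5% |
| 37 | 13.3% | 58.6% |
| 38 | 18.6% | 56.9% |
| 39 | 24.8% | 55.2% |

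From n = 37 the stated 10% is exceeded, and 26 successes would pass the rule while the exact lower limit lies below 60%. Keeping type I error within 10% would need cut-offs of 27/37, 28/38 or 28/39, which the plan does not give. If the extra patients could only count as failures, type I error would stay at 9.0%. If nobody were replaced and the first 36 treated were counted, n would remain 36.

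**Step 3: unknown 3-year status.** With k patients unknown and scored as failures, success needs 26 of the other 36 − k. Assuming loss unrelated to outcome:

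| k unknown | Power, P(X ≥ 26 given 36 − k, 0.80) | Type I error, P(X ≥ 26 given 36 − k, 0.60) |
|---|---|---|
| 0 | 91.1% | 9.0% |
| 1 | 85.4% | 5.8% |
| 2 | 77.3% | 3.4% |
| 3 | 66.6% | 1.9% |

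This scoring is conservative: the cost falls on power.

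**The case against.** The strongest reply is that the plan already settles the decision. Section 10.2 counts out of all 36, so a patient not known to be alive and progression-free is not a success. Section 10.3.1 makes the count decisive and adds Kaplan-Meier only as a supplement. Any fixed-count design assumes that all outcomes are observed. Follow-up continues to 4 years after every listed reason for stopping treatment except withdrawal of consent, so little loss is planned for. All of this stands.

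A reader might infer more: that the sample size or the 90% power is wrong, or that missing data leave the decision open to choice. The documents do not support that. The design is correct with complete data, and no passage suggests scoring an unknown patient as progression-free.

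Nor should much rest on an example in which the count fails and an estimate beside it looks favourable. With 25 progression-free and 2 unknown patients left out, 25/34 has a lower 90% limit of 61.5%, above the null, while 25/36 has 57.6%. With only one left out, 25/35 gives 59.4%. The two-sided 90% interval, which is also planned, has a lower bound of 58.4% for 25/34. The contrast needs a narrow set of counts and one choice of limit.

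It is also fair that a Kaplan-Meier curve can be read at three years. Appendix IV records that Amendment 1 moved the primary time point from 2 to 3 years as a clerical correction, so the two-year target may be a remnant. That explains the mismatch but leaves the current text naming the wrong time point.

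The reply does not reach the use of the 2-year count for the primary hypothesis or the conflict over who the 36 are.

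**Conclusion.** The point holds as a mismatch between the primary endpoint and its planned analysis. Three parts are wrong as written: Kaplan-Meier PFS is specified only at two years, the 2-year count is sent to a rule built for three years, and the evaluable population differs between the Study Summary and Section 3.0 on one side and Section 6.1 on the other.

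The population conflict carries the clearest risk to the error rate: 13.3% to 24.8% in place of 9.0%. Those figures assume that one to three replaced patients are counted as well, that each has the same 60% chance of success, and that the cut-off stays at 26.

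The unknown-status part is a clarification. The power figures of 85.4%, 77.3% and 66.6% assume both a number lost, which the documents do not give, and loss unrelated to outcome. If those lost would have progressed anyway, scoring them as failures costs no power. They do not show that the trial is underpowered.

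**What to change.** 1. **Section 10.3.1, Kaplan-Meier.** Specify the three-year PFS estimate with a 90% confidence limit; the two-year estimate may stay as descriptive. Censor event-free patients at the last assessment of progression status. Call this a supporting analysis that does not override the count.
2. **Section 10.3.1, hypothesis.** State that only the 3-year count is used for the 10.2 rule and that the 2-year proportion is descriptive.
3. **Population.** Reconcile the Study Summary and Section 3.0 with Section 6.1, so that one set of 36 serves both the count and the exact interval, and name 36 as the denominator of the 3-year proportion.
4. **Section 10.2, unknown status.** State that unknown 3-year status counts as not progression-free, and define unknown, including how off-treatment patients with no 3-year scan are classed. Add that the 90% power assumes complete 3-year status. Any figures for 1, 2 or 3 unknown patients should be labelled as illustrations that assume loss unrelated to outcome.

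The cost is wording only: no added visits, scans or patients, and the 26-of-36 rule is unchanged. The downsides are that the stated power becomes conditional and that the Kaplan-Meier estimate relies on non-informative censoring, which is one reason to keep it as support.
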